15.3. Headache Impact Test (HIT-6 v1.0)

HIT-6™

HEADACHE IMPACT TEST

This questionnaire was designed to help you describe and communicate the way you feel and what you cannot do because of headaches.

To complete, please check one box for each question.

1. When you have headaches, how often is the pain severe?

Never Rarely Sometimes Very Often Always

2. How often do headaches limit your ability to do usual daily activities including household work, work, school, or social activities?

Never Rarely Sometimes Very Often Always

3. When you have a headache, how often do you wish you could lie down?

Never Rarely Sometimes Very Often Always

4. In the past 4 weeks, how often have you felt too tired to do work or daily activities because of your headaches?

Never Rarely Sometimes Very Often Always

5. In the past 4 weeks, how often have you felt fed up or irritated because of your headaches?

Never Rarely Sometimes Very Often Always

6. In the past 4 weeks, how often did headaches limit your ability to concentrate on work or daily activities?

Never Rarely Sometimes Very Often Always

15.4. Short-Form Health Survey (SF-36 v2.0)

Sample Short-Form Health Survey (SF-36 v2.0)

This survey asks for your views about your health. This information will help you keep track of how you feel and how well you are able to do your usual activities.

Please answer every question. Some questions may look like others, but each one is different. Please take the time to read and answer each question carefully, and click on the circle that best describes your answer. *Thank you for completing this survey!*

1) In general, would you say your health is:

Excellent	Very good	Good	Fair	Poor
●	●	●	●	●

2) Compared to one year ago, how would you rate your health in general now?

Much better now than one year ago	Somewhat better now than one year ago	About the same as one year ago	Somewhat worse now than one year ago	Much worse now than one year ago
●	●	●	●	●

3) The following questions are about activities you might do during a typical day. Does your health now limit you in these activities? If so, how much?

	Yes, limited a lot	Yes, limited a little	No, not limited at all
a. Vigorous Activities , such as running, lifting heavy objects, participating in strenuous sports	●	●	●
b. Moderate Activities , such as moving a table, pushing a vacuum cleaner, bowling, or playing golf	●	●	●
c. Lifting or carrying groceries	●	●	●
d. Climbing several flights of stairs	●	●	●
e. Climbing one flight of stairs	●	●	●
f. Bending, kneeling, or stooping	●	●	●
g. Walking more than a mile	●	●	●
h. Walking several hundred yards	●	●	●
i. Walking one hundred yards	●	●	●

j. Bathing or dressing yourself

4) During the past 4 weeks, how much of the time have you had any of the following problems with your work or other regular daily activities as a result of your physical health?

	All of the time	Most of the time	Some of the time	A little of the time	None of the time
a. Cut down on the amount of time you spent on work or other activities	●	●	●	●	●
b. Accomplished less than you would like	●	●	●	●	●
c. Were limited in the kind of work or other activities	●	●	●	●	●
d. Had difficulty performing the work or other activities (for example, it took extra effort)	●	●	●	●	●

5) During the past 4 weeks, how much of the time have you had any of the following problems with your work or other regular daily activities as a result of any emotional problems (such as feeling depressed or anxious)?

	All of the time	Most of the time	Some of the time	A little of the time	None of the time
a. Cut down on the amount of time you spent on work or other activities	●	●	●	●	●
b. Accomplished less than you would like	●	●	●	●	●
c. Did work or activities less carefully than usual	●	●	●	●	●

6) During the past 4 weeks, to what extent has your physical health or emotional problems interfered with your normal social activities with family, friends, neighbors, or groups?

Not at all Slightly Moderately Quite a bit Extremely

7) How much bodily pain have you had during the past 4 weeks?

None	Very Mild	Mild	Moderate	Severe	Very Severe
●	●	●	●	●	●

8) During the past 4 weeks, how much did pain interfere with your normal work (including both work outside the home and housework)?

Not at all	A little bit	Moderately	Quite a bit	Extremely
●	●	●	●	●

9) These questions are about how you feel and how things have been with you during the past 4 weeks. For each question, please give the one answer that comes closest to the way you have been feeling. How much of the time during the past 4 weeks...

	All of the time	Most of the time	Some of the time	A little of the time	None of the time
a. Did you feel full of life?	●	●	●	●	●
b. Have you been very nervous?	●	●	●	●	●
c. Have you felt so down in the dumps that nothing could cheer you up?	●	●	●	●	●
d. Have you felt calm and peaceful?	●	●	●	●	●
e. Did you have a lot of energy?	●	●	●	●	●
f. Have you felt downhearted and depressed?	●	●	●	●	●
g. Did you feel worn out?	●	●	●	●	●
h. Have you been happy?	●	●	●	●	●
i. Did you feel tired?	●	●	●	●	●

10) During the past 4 weeks, how much of the time has your physical health or emotional problems interfered with your social activities (like visiting friends, relatives, etc.)?

All of the time Most of the time Some of the time A little of the time None of the time

11) How TRUE or FALSE is each of the following statements for you?

	Definitely true	Mostly true	Don't know	Mostly false	Definitely false
a. I seem to get sick a little easier than other people	●	●	●	●	●
b. I am as healthy as anybody I know	●	●	●	●	●
c. I expect my health to get worse	●	●	●	●	●
d. My health is excellent	●	●	●	●	●

15.5. Health Related Quality of Life (EQ-5D-5L)

Health Questionnaire

English version for the USA

USA (English) © 2009 EuroQol Group EQ-5D™ is a trade mark of the EuroQol Group

Under each heading, please check the ONE box that best describes your health TODAY.

MOBILITY

I have no problems walking	
I have slight problems walking	
I have moderate problems walking	
I have severe problems walking	
I am unable to walk	

SELF-CARE

I have no problems washing or dressing myself	
I have slight problems washing or dressing myself	
I have moderate problems washing or dressing myself	
I have severe problems washing or dressing myself	
I am unable to wash or dress myself	

USUAL ACTIVITIES (e.g. work, study, housework, family or leisure activities)

I have no problems doing my usual activities	
I have slight problems doing my usual activities	
I have moderate problems doing my usual activities	
I have severe problems doing my usual activities	
I am unable to do my usual activities	

PAIN / DISCOMFORT

[figure not shown]
I have no pain or discomfort	
I have slight pain or discomfort	
I have moderate pain or discomfort	
I have severe pain or discomfort	
I have extreme pain or discomfort	

ANXIETY / DEPRESSION

I am not anxious or depressed	
I am slightly anxious or depressed	
I am moderately anxious or depressed	
I am severely anxious or depressed	
I am extremely anxious or depressed	

- We would like to know how good or bad your health is TODAY.
- This scale is numbered from 0 to 100.
- 100 means the best health you can imagine.
0 means the worst health you can imagine.
- Mark an X on the scale to indicate how your health is TODAY.
- Now, please write the number you marked on the scale in the box below.

YOUR HEALTH TODAY =

15.6. Patient Global Impression of Change (PGIC)

Patient Global Impression of Change (PGIC)

This section to be completed by site staff

Protocol: ALD403-CLIN-013 Subject #: _____ Visit Date: _____

Visit (please check one):

Week 4 Week 8 Week 12 Week 24 Week 36
 Week 48 Week 56 or ET Week 60 Week 72 Week 84
 Week 104 or ET

Since first receiving study drug in this study, how would you describe the change (if any) in ACTIVITY LIMITATIONS, SYMPTOMS, EMOTIONS and OVERALL QUALITY OF LIFE, as related to your migraine? Choose ONE.

____ Very Much Improved
____ Much Improved
____ Minimally Improved
____ No Change
____ Minimally Worse
____ Much Worse
____ Very Much Worse

Version Date: 17 Nov 2017

15.7. Most Bothersome Symptom (MBS)

Most Bothersome Symptom (MBS)

This section to be completed by site staff at each visit, Screening through Week 56, or ET

Protocol: ALD403-CLIN-013 Subject #: _____ Visit Date: _____

Visit (please check one):

Screen Day 0 Week 4 Week 8 Week 12
 Week 24 Week 36 Week 48 Week 56 or ET

Most Bothersome Symptom (as noted by subject at screening visit): _____

This section to be completed by subject at each visit, Day 0 through Week 56, or ET

Since beginning this study, how would you describe the change (if any) in your most bothersome symptom? Choose ONE.

____ Very Much Improved
____ Much Improved
____ Minimally Improved
____ No Change
____ Minimally Worse
____ Much Worse
____ Very Much Worse

Version Date: 16 SEP 2016

15.8. The Migraine Disability Assessment (MIDAS)

MIDAS QUESTIONNAIRE

INSTRUCTIONS: Please answer the following questions about ALL the headaches you have had over the last 3 months. Write your answer in the box next to each question. Write zero if you did not do the activity in the last 3 months. (Please refer to the calendar below, if necessary.)

1. On how many days in the last 3 months did you miss work or school because of your headaches? days
2. How many days in the last 3 months was your productivity at work or school reduced by half or more because of your headaches? (Do not include days you counted in question 1 where you missed work or school) days
3. On how many days in the last 3 months did you not do household work because of your headaches? days
4. How many days in the last 3 months was your productivity in household work reduced by half or more because of your headaches? (Do not include days you counted in question 3 where you did not do household work) days
5. On how many days in the last 3 months did you miss family, social, or leisure activities because of your headaches? days

A. On how many days in the last 3 months did you have any headache?
(If a headache lasted more than one day, count each day) days

B. On a scale of 0 - 10, on average how painful were these headaches?
(where 0 = no pain at all, and 10 = pain which is as bad as it can be)

mg	Milligram
MIDAS	Migraine Disability Assessment
mL	Milliliter
mm	Millimeter
MRM	Menstrually-related migraine
NOAEL	No-observed-adverse-effect-level
NSAID	Non-steroidal anti-inflammatory drug
PI	Principal Investigator
PK	Pharmacokinetic
PGIC	Patient Global Impression of Change
PRO	Patient Reported Outcome
QTcF	QT corrected using Fridericia formula
RBC	Red blood cell
SAE	Serious adverse event
SF-36	Short Form Health Survey
TMD	Temporomandibular Disorder
WBC	White blood cell

1 CLINICAL TRIAL DESCRIPTION

Migraine is a highly prevalent paroxysmal neurological disease characterized by recurrent episodes of moderate to severe headache associated with physiological disruptions of neurological, gastrointestinal, and sensory function. Episodes typically last between 4 and 72 hours and recur often without warning over decades of time.

Generally, migraine begins as an episodic disease. Between episodes of migraine the nervous system returns to a normal (premorbid) state of function. However, approximately 2.5% of people with episodic migraine will annually transform from episodic to chronic migraine, meaning they are experiencing migraine on greater than 15 days per month for at least 3 consecutive months.¹ For those with chronic migraine, the headaches are more intense; migraine-associated symptoms, more severe; and the disease-related impact and disability are much greater than observed for episodic migraine.² In addition, chronic migraine is associated with more co-morbid diseases such as anxiety, depression, and non-headache pain.³

Calcitonin gene-related peptide (CGRP) is a member of the calcitonin family of peptides and is thought to have a multiplicity of actions within the brain, including the facilitation of pain transmission and the induction of the nociceptive state, both of which may contribute to the mechanism of migraine^{4, 5}. ALD403 is a humanized anti-(calcitonin gene-related peptide) monoclonal antibody (anti-CGRP) that binds to CGRP and is being developed by Alder BioPharmaceuticals, Inc. for the prophylaxis of migraine.

1.1 Objectives

1.1.1 Safety Objective

The primary objective is:

- To evaluate the long term safety of repeat doses of ALD403 administered intravenous (IV) in patients with chronic migraine.

1.1.2 Immunogenicity and Patient Reported Outcomes Objectives

The secondary objectives include the following:

- To evaluate the pharmacokinetics (PK) and immunogenicity of repeat doses of ALD403 administered IV to patients with chronic migraine.
- To further evaluate the impact of ALD403 on various patient reported outcomes.

1.2 Clinical Trial Design

This is an open label trial which will include two treatment phases. The primary treatment phase will include four intravenous infusions of 300mg ALD403 in patients with chronic migraine. Infusions will be 12 weeks apart. The secondary treatment phase will include four additional 300mg ALD403 infusions 12 weeks apart. Subjects who provide informed consent will be evaluated for eligibility based upon the inclusion and exclusion criteria.

Eligible subjects will receive 4 IV infusions of 300mg ALD403 in the primary treatment phase on Days 0 (11-14 days after the screening visit), 84 (Week 12), 168 (Week 24) and 252 (Week 36). Subjects who receive all 4 infusions in the primary treatment phase may enter the secondary treatment phase, where subjects will receive up to 4 additional infusions for a total of 8 infusions. The infusions in the secondary treatment phase will occur on Days 336 (Week 48), 420 (Week 60), 504 (Week 72) and 588 (Week 84). Subjects will be followed for 20 weeks until Week 104 for a total study duration of approximately 106 weeks, including the screening period. Subjects who don't receive all 4 infusions of ALD403 in the primary treatment phase or don't consent for participation in the secondary treatment phase will be followed at Week 48 and Week 56, at which point they will have their End of Trial visit.

Approximately 120 subjects will be enrolled and treated. Study specific assessments will be conducted according to the Schedule of Events presented in [Table 1: Schedule of Events and Assessment](#).

1.3 Sample Size

The planned sample size for this study is 120 treated subjects. It is assumed that over 75% of these subjects will complete the primary treatment phase resulting in at least 90 subjects with one year of safety data collection.

TABLE 1: SCHEDULE OF EVENTS AND ASSESSMENT

Assessments	Screening Day -14 to -11	Day 0	Wk 2 Day 14 ± 3 days	Wk 4 Day 28 ± 3 days	Wk 8 Day 56 ± 3 days	Wk 12 & 24 & 36 Day 84 / 168 / 252 ± 3 days	Wk 48 Day 336 -7/+14 days	Wk 60 & 72 & 84 Day 420 / 504 / 588 ± 7 days	Wk 56 ⁹ or 104 EOT / Early Withdrawal Day 392 or 728 ± 7 days
Informed Consent, Demographics, Medical History, Height	X								
In/Ex Criteria	X	X							
Weight	X	X				X			X
Physical Exam ¹	X	X				X	X ¹¹	X	X
Vital Signs ³	X	X				X	X	X	X
C-SSRS ^{4,1}	X	X	X	X	X	X	X	X	X
PGIC ²				X	X	X	X	X	X
SF-36, HIT-6 ¹	X	X		X		X	X	X	X
EQ-5D-5L ¹²	X	X		X		X	X		X ¹⁰
MBS	X	X		X	X	X	X		X ¹⁰
MIDAS ¹		X				X	X	X	X
AE/ Con Med Review	X	X	X	X	X	X	X	X	X
ALD403 infusion ⁵		X				X	X ¹¹	X	
12-lead ECG ⁷	X	X				X	X	X	X
Hematology, Chemistry ¹	X	X				X	X	X	X
HIV/Hepatitis B and C	X								
Plasma PK ^{6,8}		X	X	X	X	X	X		X
Serum Anti-ALD403 ⁶		X	X	X	X	X	X		X
Urine Drugs of Abuse ¹	X								
Urine Pregnancy Test	X	X		X	X	X	X	X	X

¹ Conduct assessment pre-dose on Day 0 and Week 12, 24, 36, 48, 60, 72, and 84.

² Conduct assessment pre-dose on Week 12, 24, 36, 48, 60, 72, and 84.

³ Conduct assessments pre-dose and up to 2 hours (+ 30 min) post-dose on Day 0 and Week 12, 24, 36, 48, 60, 72, and 84.

⁴ Conduct **C-SSRS Baseline/Screening Version** at screening and **C-SSRS Since Last Visit Version** at remaining visits where C-SSRS required.

⁵ Monitor subjects for at least 2 hours after the end of each dosing to assess for the occurrence of adverse events.

⁶ Collect samples pre-dose on Day 0 and Week 12, 24, 36, 48, and 72. Subjects who test positive for anti-ALD403 antibodies at the last study visit will be asked to provide up to 2 additional blood samples for immunogenicity testing at 3 month intervals for up to 6 months.

⁷ Conduct assessment pre-dose, and within 2 hours (+ 30 min) post dose on Day 0 and Week 12, 24, 36, 48, 60, 72, and 84.

⁸ On Day 0, collect additional sample immediately post-dose (within 15 minutes of end of infusion).

⁹ Subjects who don't received all 4 infusions of ALD403 in the primary treatment phase or don't consent to participate in the secondary treatment phase will have the End of Trial/Early Withdrawal visit at Week 56.

¹⁰ Only for subjects who have the End of Trial/Early Withdrawal visit at Week 56.

¹¹ Only for subjects who participate in secondary treatment phase.

¹² Conduct assessment pre-dose on Day 0 and Week 12, 24, 36, and 48.

2 STATISTICAL METHODS

2.1 *Populations Analyzed*

The analysis populations are defined as the following:

- Safety Population – Includes all subjects who received at least one dose of treatment.
- PK Population - All subjects who have at least one reportable plasma concentration. The PK population will be used for PK analyses.

2.2 *Clinical Trial Endpoints*

The safety, pharmacokinetic and immunogenicity of ALD403 will be assessed using the following endpoints. Greater detail concerning these endpoints can be found in [Section 2.2.1](#).

Safety Endpoints

- Adverse events (AEs) and serious adverse events (SAEs)
- Clinical laboratory assessments
- Vital signs
- Electrocardiograms (ECGs)
- Columbia-Suicide Severity Rating Scale (C-SSRS)

Patient Reported Outcomes:

- Patient Global Impression of Change (PGIC)
- Short-Form Health Survey (SF-36)
- Health-Related Quality of Life (EQ-5D-5L)
- Headache Impact Test (HIT-6)
- Most Bothersome Symptom (MBS)
- The Migraine Disability Assessment (MIDAS)

Pharmacokinetic and Immunogenicity Endpoints

- Free ALD403 plasma concentrations
- Development of specific anti-ALD403 antibodies
- Characterization of specific anti-ALD403 antibodies for neutralizing activity

2.2.1 Questionnaires

Patient Global Impression of Change (PGIC)

The PGIC includes a single question concerning the subject's impression of the change in their disease status since the start of the study. Seven responses are possible: Very Much Improved, Much Improved, Minimally Improved, No Change, Minimally Worse, Much Worse, Very Much Worse.

SF-36 Health Survey (SF-36 v2.0)

The SF-36 v2.0 is a health survey containing 36 questions consisting of eight scaled scores to measure quality of life over the past 4 weeks. The eight sections measured are vitality, physical functioning, bodily pain, general health perceptions, physical role functioning, emotional role functioning, social role functioning, and mental health. Scoring software utilizing the 2016 norm-based scoring algorithm will be used to calculate the scaled score for each of the eight sections.

EQ-5D-5L

The EQ-5D-5L is a descriptive system of health-related quality of life states consisting of five dimensions/questions (mobility, self-care, usual activities, pain/discomfort, anxiety/depression) each of which can take one of five responses. The responses record five levels of severity (no problems/slight problems/moderate problems/severe problems/extreme problems) within a particular EQ-5D dimension. The EQ-5D-5L additionally includes a VAS scale. Each item will be summarized separately.

Headache Impact Test (HIT-6 v1.0)

The Headache Impact Test (HIT) is a tool used to measure the impact and effect on the ability to function normal in daily life when a headache occurs. The HIT is a 6 question, Likert-type, self-

reporting questionnaire with responses ranging from “Never” to “Always” with the following response scores: Never=6, Rarely=8, Sometimes=10, Very Often=11, Always=13. The total score for the HIT is the sum of each response score and will be treated as missing if the response is missing for one or more questions. The HIT total score ranges from 36 to 78, with score ranges having the following life impact:

Score Range	Life Impact
>= 60	Severe
56-59	Substantial
50-55	Some
<= 49	Little to None

Most Bothersome Symptom (MBS)

At screening subjects will identify migraine related symptom that is most bothersome for them. Subjects will be asked to rate the improvement in this symptom from screening on a seven-point scale identical to the scale used for the PGIC.

The Migraine Disability Assessment (MIDAS)

The MIDAS questionnaire measures the effect headaches have on the subject’s daily functioning. Midas is composed of five questions that ask about the subject’s performance over the past 3 months. The response to each question is provided in number of days which are totaled to determine the level of disability:

Score Range	Level of Disability
0-5	Grade I, Little or no disability
6-10	Grade II, Mild disability
11-20	Grade III, Moderate disability
21+	Grade IV, Severe disability

2.2.2 Pharmacokinetics

The concentrations of ALD403 will be measured in plasma from all treated subjects using a validated assay. The PK analysis will include evaluations of concentration-time profiles for free ALD403 on Day 0 (pre-dose and immediately post-dose (within 15 minutes of end of infusion)),

and Weeks 2, 4, 8, 12 (pre-dose), 24 (pre-dose), 36 (pre-dose), 48 (pre-dose), 72 (pre-dose) and 104 or ET.

If a subject terminates early from the clinical trial, all efforts will be made to collect blood samples to analyse for free ALD403 unless consent has been withdrawn.

2.2.3 Immunogenicity

Serum blood samples will be taken pre-dose on Day 0, and Weeks 2, 4, 8, 12 (pre-dose), 24 (pre-dose), 36 (pre-dose), 48 (pre-dose), 72 (pre-dose), and 104 or ET to test for the development of antibodies to ALD403. The immunogenicity will be assessed in serum from all ALD403-treated subjects using a validated assay.

For any samples that are positive for anti-ALD403 antibody, there may be additional testing to characterize the anti-ALD403 antibody for the potential to neutralize (NAb) ALD403 activity. Subjects who test positive for specific anti-ALD403 antibodies at the time of the last study visit will be asked to provide up to 2 additional blood samples for immunogenicity testing at 3 month intervals for up to 6 months.

2.3 Trial Day

Trial endpoints will be reported within analysis windows based upon the actual date of the assessment. Assignment of results to these time points is based upon the trial day. Trial day is defined as:

Trial day = date of assessment - date of treatment

Analysis Windows used to report endpoints are outlined in [Table 2](#)

TABLE 2: ANALYSIS WINDOWS

Visit	Range	Target Day	If more than one which one is used for analyses
Screening	< Day 0		First value
Day 0	Day 0 to Day 7	Day 0	Closest to Target Day
Week 2	Day 8 to Day 21	Day 14	Closest to Target Day
Week 4	Day 22 to Day 42	Day 28	Closest to Target Day
Week 8	Day 43 to Day 70	Day 56	Closest to Target Day
Week 12	Day 71 to Day 126	Day 84	Closest to Target Day
Week 24	Day 127 to Day 204	Day 168	Closest to Target Day

Week 36	Day 205 to Day 288	Day 252	Closest to Target Day
Week 48	Day 289 to Day 378	Day 336	Closest to Target Day
Week 60	Day 379 to Day 462	Day 420	Closest to Target Day
Week 72	Day 463 to Day 546	Day 504	Closest to Target Day
Week 84	Day 546 to Day 630	Day 588	Closest to Target Day
Week 104	> Day 630	Day 728	Closest to Target Day

Note: If two observations are equidistant to the target day, the first observation is used.

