3.3.6 Clinical Trial Treatment

Total volume infused, number of infusions and reason for dose interruption will be listed as well as summarized in a table.

3.4 *Efficacy Analyses*

The secondary endpoints of patient reported outcomes (PROs) will be summarized with descriptive statistics by time point. These summary measures will be based upon the observed results and where appropriate the change from baseline results. The denominator for percentages will be the total number of PROs collected at each visit since not all subjects will complete PROs at all visits.

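### SAP Table 2 has no Week 56 window, so the End of Trial visit of subjects who do not continue is reported, and its PRO scores are t-tested, as Week 60

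*SAP*

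**What the plan says.** SAP 1.2 says that subjects who miss a primary-phase infusion, or do not consent to the secondary phase, "will be followed at Week 48 and Week 56, at which point they will have their End of Trial visit". The last column of SAP Table 1 dates this visit: "Early Withdrawal Day 392 or 728 ± 7 days". The protocol's Schedule of Events agrees. The protocol's PGIC form (15.6) treats Week 56 and Week 60 as different visits, with separate boxes: "Week 48 Week 56 or ET Week 60 Week 72 Week 84".

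SAP 2.3 then sets the reporting rule: "Trial endpoints will be reported within analysis windows based upon the actual date of the assessment". In Table 2 the Week 48 window ends at Day 378 and the next row is Week 60, "Day 379 to Day 462", target Day 420. There is no row for Week 56 or for End of Trial.

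The Week 56 visit collects SF-36, HIT-6, MIDAS, PGIC, laboratory tests, vital signs, ECG, PK and antibody samples. It also collects EQ-5D-5L and MBS, which at End of Trial are taken "Only for subjects who have the End of Trial/Early Withdrawal visit at Week 56" (SAP Table 1, footnote 10) and are not scheduled at Week 60. SF-36 component scores and HIT-6 and MIDAS totals are t-tested for change from baseline at Week 60, among other visits (SAP 3.4.2, 3.4.5, 3.4.6; protocol 13.4.2). For PRO percentages, SAP 3.4 says "The denominator for percentages will be the total number of PROs collected at each visit".

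**The concern.** Applied as written, the rule gives a separately scheduled visit the label of a visit these subjects never had. The Week 60 PRO means, t-tests and PGIC percentages would then combine two groups at different times after dosing, and the table would not show it. Laboratory, vital-sign and ECG summaries by visit would merge in the same way.

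For EQ-5D-5L and MBS the fault is different. Neither is scheduled at Week 60, so a Week 60 row would hold essentially Week 56 data under the wrong name.

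Two further consequences are possible but not certain. End of Trial PK and antibody samples could produce a Week 60 row although SAP 2.2.2, 2.2.3 and 3.5 list no Week 60 sample. Follow-up antibody samples, taken only from subjects positive at their last visit, fall on days that Table 2 assigns to Weeks 72 and 84. If they were counted, subjects selected for being positive would raise the Week 72 percentage. PROs and immunogenicity are secondary objectives.

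**Working it through.** **Inputs.** Table 2 windows and targets (SAP 2.3); Week 56 visit at Day 392 ± 7 (SAP Table 1); infusion days and visit windows (protocol synopsis and SAP Table 1); 120 treated subjects with over 75% completing the primary phase (SAP 1.3). Trial day is counted from the first infusion. SAP 2.3 does not say which infusion, but targets up to Day 728 require the first.

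**The plan's own window.** Midpoints between adjacent targets are (336 + 420)/2 = 378 and (420 + 504)/2 = 462. These give Days 379 to 462 for Week 60, exactly as stated. The Week 56 target, 56 × 7 = Day 392, played no part in setting these limits.

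**Where Week 56 lands.** The permitted days are 392 − 7 = 385 to 392 + 7 = 399, which is 15 days. All 15 lie within 379 to 462 and none in another window. Their distance from the Week 60 target is 420 − 399 = 21 to 420 − 385 = 35 days. The nearest-to-target rule does not remove them, because these subjects have no Week 60 visit and this is normally their only record in the window.

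**Time since last infusion.**

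| Group | Calculation | Weeks |
|---|---|---|
| Week 56, fourth infusion given (Days 249–255), nominal | (392 − 252)/7 | 20.0 |
| Same, range | (385 − 255)/7 to (399 − 249)/7 | 18.6 to 21.4 |
| Week 56, last infusion at Week 24, nominal | (392 − 168)/7 | 32.0 |
| Week 60, fifth infusion given (Days 329–350), nominal | (420 − 336)/7 | 12.0 |
| Same, range | (413 − 350)/7 to (427 − 329)/7 | 9.0 to 14.0 |

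The two ranges, 18.6–21.4 and 9.0–14.0 weeks, do not overlap.

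**Share of the Week 60 row.** The documents do not give the number of Week 56 attendees. From "It is assumed that over 75% of these subjects will complete the primary treatment phase", 120 × 0.75 = 90 completers. Assume that 90 continue and attend Week 60, and that 10, 20 or 30 others attend Week 56. The shares are 10/100 = 10%, 20/110 = 18% and 30/120 = 25%. If instead all 120 attend one visit or the other and 10, 20, 30 or 40 of them attend Week 56, the shares are 8.3%, 16.7%, 25.0% and 33.3%. The reported mean moves by the share times the difference between the two groups; the documents give no such difference.

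**Antibody follow-up.** Taking three months as 91 days, samples fall on Days 385 + 91 = 476 to 399 + 91 = 490, all in Week 72, and on Days 385 + 182 = 567 to 399 + 182 = 581, all in Week 84.

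**A date-based Week 56 window.** The midpoints (336 + 392)/2 = 364 and (392 + 420)/2 = 406 give Week 48 as Days 289–364, Week 56 as Days 365–406 and Week 60 as Days 407–462. All permitted days for Week 48 (329–350), Week 56 (385–399) and Week 60 (413–427) then fall in their own windows.

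**The case against.** The strongest reply concerns the stakes. This is a single-arm, open-label safety study. The affected tests are one visit in a series of eight on secondary PROs, with no alpha, success rule or group comparison attached, and no bias of known size or direction has been shown. That is correct, and it limits the seriousness.

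Second, Table 2 is deliberately wide. Week 60 accepts values 41 days before and 42 days after its target, and Week 104 opens at Day 631, 97 days before Day 728. Subjects off treatment are also encouraged to stay in assessment, so mixed times since dosing occur elsewhere by design. This is also true, but wide windows are meant for late or early attendance at the named visit. Here a different scheduled visit is absorbed on every day it may be held.

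Third, the share is an assumption. It is not an upper bound, because subjects who complete the primary phase may decline the secondary phase. It may also be too high, because some subjects will withdraw or be lost. Both points stand.

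Fourth, the sampling-time lists give the last PK and antibody time as Week 104 or early termination, SAP 3.5 defers further PK analyses to a separate plan, and SAP 3.6.5 can be read to exclude samples taken after the trial. The PK and antibody consequences therefore remain possibilities that the SAP should close off.

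**Conclusion.** The concern holds. On the SAP's literal rule every in-window Week 56 visit, 15 of 15 permitted days, is reported as Week 60. No passage exempts End of Trial visits or limits the Week 60 summaries to secondary-phase subjects. The mislabelling is certain. The weight of Week 56 data in the Week 60 results is not known; 10% to 25% is illustrative and rests on 90 subjects continuing and 10 to 30 attending Week 56. The effect on any estimate cannot be sized from the documents. The primary safety objective is touched only through the by-visit laboratory, vital-sign and ECG summaries. This should be corrected before the analysis is run, but it does not threaten the trial's main conclusions.

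**What to change.** - Add a Table 2 row for Week 56 / End of Trial, restricted to non-continuing subjects and assigned by nominal visit. Keep those records out of the Week 60 summaries and t-tests. If a date rule is preferred, Days 365–406 works, provided it applies only to subjects whose End of Trial visit is Week 56; otherwise an early Week 60 visit by a continuing subject could be moved into it.
- State that EQ-5D-5L and MBS have no Week 60 row.
- State where End of Trial PK and antibody samples are reported, consistently with SAP 2.2.2, 2.2.3 and 3.5.
- State that antibody follow-up samples taken after the last study visit go in a separate row or listing, outside the visit denominators.
- As a separate small correction, start the Week 84 window at Day 547, since Day 546 is now in both Week 72 and Week 84.

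The cost is one table row, a few sentences and a little programming. Under the assumption above, the Week 60 n falls from 100–120 to 90, with the removed values shown under their own visit.
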